#### 1. RCT Details

This section provides a high-level overview of an **ongoing** RCT that the described real-world evidence study is trying to replicate as closely as possible given the limitations inherent in the healthcare databases.

#### 1.1 Title

# Comparison of Bleeding Risk Between Rivaroxaban and Apixaban in Patients with Atrial Fibrillation (COBRRA - AF)

#### 1.2 Intended aim(s)

To compare the incidence of major and clinically relevant non-major bleeding events in patients with non-valvular atrial fibrillation diagnosed by an ECG.

#### 1.3 Primary endpoint for replication

Time from randomization to the first confirmed, adjudicated occurrence of a major bleeding or clinically relevant non-major bleeding event up to 365 days after initiating anticoagulation treatment.

#### 1.4 Required power for primary endpoint and noninferiority margin (if applicable)

The hazard ratio for the clinical trial is unknown because the trial is ongoing. Based upon Proietti et al., a systematic review of observational studies of apixaban safety in atrial fibrillation patients, we calculated power based on an array of potential effect sizes.

#### 1.5 Secondary endpoint for replication (assay sensitivity) and RCT finding Secondary cardiovascular objectives:

- To assess the frequency of major bleeding events and non-major clinically relevant bleeding events as separate outcomes
- Stroke
- All-cause mortality

#### 1.6 Trial estimate

The trial is ongoing and scheduled to complete in December of 2025.

#### 3. Data Source(s)

Optum CDM, IBM® MarketScan®, CMS NOAC

#### 4. Study Design Diagram

The study design diagram visualizes key aspects of the longitudinal study design for expedited review.

Figure 1.

#### 5. Cohort Identification

#### 5.1 Cohort Summary

An active-comparator, new-user design, propensity score matched, cohort study will be applied to compare patients that received apixaban vs. rivaroxaban. Patients will enter the cohort upon initiation of apixaban or rivaroxaban after a 180 day washout without anticoagulant exposure. They will be required to have a diagnosis code indicating non-valvular atrial fibrillation in the prior 180 days, and be age 18 or older on the date of initiation of therapy. Subjects will be excluded if they have had any indication of stage IV or V CKD, ESRD, an active bleeding episode, cancer, obesity, liver disease, or another indication for long-term anticoagulation, such as hospitalization for DVT or PE, in the prior 180 days. Patients will also be excluded if they have used any contraindicated medications in the prior 180 days or had an indication for atrial fibrillation that was not non-valvular. All patients were required to have continuous enrollment for 180 days prior to cohort entry to ensure incident use of the study drugs.

#### 5.2 Important steps for cohort formation

New use of the exposure (apixaban or rivaroxaban) is defined as no use of either drug in the 180 days prior to cohort entry. The first eligible cohort entry date will be selected after applying all inclusion-exclusion criteria.

#### 5.2.1 Eligible cohort entry dates

The apixaban indication for prevention of stroke or systemic embolism in patients with atrial fibrillation was approved by the FDA on December 28th, 2012. Rivaroxaban was initially approved for the same indication on November 4th, 2011.

- IBM® MarketScan®: Dec 28, 2012 December 31, 2019 (end of available data)
- Optum CDM: Dec 28, 2012 June 30, 2020 (end of available data)
- CMS NOAC: Dec 28, 2012 Dec 31, 2017 (end of available data)

#### 5.2.2 Specify inclusion/exclusion criteria for cohort entry and define the index date

Inclusion and exclusion criteria were adapted from the trial as closely as possible. Definitions for all inclusion/exclusion are provided in **Appendix** and are summarized in the flowcharts below.

#### 5.3 Flowchart of the study cohort assembly For Apixaban vs. Rivaroxaban

	0	ptum CDM	IBM® M	arketScan®	CMS - NOAC	
	Less Excluded Patients	Remaining Patients	Less Excluded Patients	Remaining Patients	Less Excluded Patients	Remaining Patients
All patients in our database		81,796,156		205,537,714		6,886,908
Patients with Apixaban/Rivaroxaban [measured between Dec 28, 2012 and June 30, 2020.]		856,974		685,749		2,232,416
Excluded due to insufficient enrollment [-180, 0]	-118,628 (14%)	738,346	-54,038 (8%)	631,711	-373,136 (17%)	1,859,280
After wash-out for prior use of reference (Rivaroxaban) [-180, -1]	-206,560 (28%)	531,786	-211,703 (34%)	420,008	-601,148 (32%)	1,258,132
After wash-out for prior use of exposure (Apixaban) [-180, -1]	-278,943 (52%)	252,843	-170,997 (41%)	249,011	-549,695 (44%)	708,437
Excluded because patient qualified in >1 exposure category	-13 (<1%)	252,830	-24 (<1%)	248,987	-54 (<1%)	708,383
Exclusion of Missing Age [-180, 0]	-7 (<1%)	252,823	-0 (<1%)	248,987	-151 (<1%)	708,232
Exclusion of Gender (Exclude Missing Values) [start of all available data, 0]	-17 (<1%)	252,806	-0 (<1%)	248,987		
Inclusion of Age >= 18 [0,0]	-170 (<1%)	252,636	-415 (<1%)	248,572		
Inclusion of Non-Valvular A-fib [- 180,0]	-104,252 (41%)	148,384	-132,025 (53%)	116,547	-264,650 (37%)	443,581
Exclusion of Anticoagulant Use [- 180, 0]	-7,414 (5%)	140,970	-6,140 (5%)	110,407	-34,042 (8%)	409,539
Exclusion of CKD Stage 4/5 or ESRD [-180,0]	-2,876 (2%)	138,094	-994 (<1%)	109,413	-7,617 (2%)	401,922
Exclusion of Dialysis or Renal Transplant) [-180, 0]	-158 (<1%)	137,936	-119 (<1%)	109,294	-421 (<1%)	401,501

Exclusion of Bleeding History [-180, 0]	-2,721 (2%)	135,215	-3,332 (3%)	105,962	-23,500 (6%)	378,001
Exclusion of Cancer [-180,0]	-5,556 (4%)	129,659	-3,177 (3%)	102,785	-14,538 (4%)	363,463
Exclusion of Weight > 120 kg [-180, 0]	-6,963 (5%)	122,696	-3,322 (3%)	99,463	-10,521 (3%)	352,942
Exclusion of Significant Liver Disease [-180, 0]	-1,781 (1%)	120,915	-892 (<1%)	98,571	-3,233 (<1%)	349,709
Exclusion of Use of Contraindicated Medications [-180, 0]	-693 (<1%)	120,222	-596 (<1%)	97,975	-2,762 (<1%)	346,947
Exclusion of Dual Antiplatelet Therapy [-180,0]	-3,219 (3%)	117,003	-2,642 (3%)	95,333	-9,829 (3%)	337,118
Exclusion of Other Heart Conditions [-180,0]	-3,603 (3%)	113,400	-3,056 (3%)	92,277	-7,962 (2%)	329,156
Exclusion of Other Indication of Long-Term Anticoagulation [-180, 0]	-489 (<1%)	112,911	-293 (<1%)	91,984	-1,447 (<1%)	327,709
Exclusion of Pregnancy [-180,0]	-3 (<1%)	112,908	-4 (<1%)	91,980		
Exclusion of Coagulopathy [-180,0]	-958 (<1%)	111,950	-320 (<1%)	91,660		
Final cohort		111,950		91,660		325,926

 $^{\ast}\text{CMS}$  cell suppression policies may result in omitted data

#### 6. Variables

#### 6.1 Exposure-related variables:

#### Study drug:

The study exposure of interest is defined by a prescription drug claim indicating apixaban dispensation. New initiation will be defined by no such records of apixaban in the prior 180 days before treatment initiation (washout period) and fulfillment of study eligibility criteria.

#### Comparator agent:

The comparator is defined by a prescription drug claim indicating rivaroxaban dispensation. New initiation will be defined by no such records of rivaroxaban in the prior 180 days before treatment initiation (washout period) and fulfillment of study eligibility criteria.

#### 6.2 Preliminary Covariates:

- Age
- Gender
- CCI score

The covariate listed above represents only a small subset of the covariate vector that will ultimately be controlled for in the design and analysis. We use the covariates above only for initial feasibility analyses to judge whether there is likely to be sufficient overlap between treatment groups to proceed with the study. Remaining covariates are defined only after the study has passed the initial feasibility analysis and the initial power assessment and are listed in Table 1 (**Appendix B**).

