#### Date conducted: 01/21/2022 and 01/28/2022

In order to complete the initial power analysis, a dummy outcome indicating a 90-day gap in database enrollment will be used. This

outcome is used to ensure that no information on the comparative risks of the outcomes of interest are available at this stage. A 1:1 PS-matched comparative analysis was performed, including age, gender, and CCI score as the only covariates. Power calculations are based on the formulas from Chow et al. (2008).

• Stop analyses until feasibility and power are reviewed by primary investigators and FDA. Reviewers evaluate the results of the analyses described above in Sections 7 and 8, including numbers of patients, patient characteristics, follow-up time, and reasons for censoring by treatment group, as well as overall rates of outcomes and study power. These parameters are re-evaluated and reported in the subsequent sections, after incorporating feedback and refining the protocol.

This emulation is of a trial that is not yet completed. The trial investigators have not published their power calculations. Therefore, we present a range of power calculations for different effect sizes given the feasibility counts and an alpha of 0.05. The range in potential hazard rations comes from a meta- analysis of safety and efficacy studies of apixaban in patients with atrial fibrillation (Proietti et al. 2017). The target enrollment for the trial is 3,028 participants. We anticipate a pooled analytic cohort of 529,536 subjects.

1. Pooled

Superiority Analysis - Pooled					
Number of patients matched	454,312	454,312	454,312	454,312	454,312
Reference	227,156	227,156	227,156	227,156	227,156
Exposure	227,156	227,156	227,156	227,156	227,156
Risk per 1,000 patients	41.4155034	41.4155034	41.4155034	41.4155034	41.4155034
Alpha (2-sided	0.05	0.05	0.05	0.05	0.05
Desired HR from RCT	0.8	0.7	0.6	0.5	0.4
Number of events expected	18815.5602	18815.5602	18815.5602	18815.5602	18815.5602
Power	1	1	1	1	1

2. Optum CDM

Superiority Analysis - Optum					
Number of patients matched	78,962	78,962	78,962	78,962	78,962
Reference	39,481	39,481	39,481	39,481	39,481
Exposure	39,481	39,481	39,481	39,481	39,481
Risk per 1,000 patients	19.8838767	19.8838767	19.8838767	19.8838767	19.8838767
Alpha (2-sided	0.05	0.05	0.05	0.05	0.05
Desired HR from RCT	0.8	0.7	0.6	0.5	0.4
Number of events expected	1570.07067	1570.07067	1570.07067	1570.07067	1570.07067
Power	0.99307189	0.99999984	1	1	1

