#### Date conducted: 02/25/2022

After review of initial feasibility and power analyses, complete creation of the remaining covariates from Section 6.2. Again, using the

dummy outcome of a 90-day gap in database enrollment, complete a 1:1 PS-matched analysis. The PS should include the complete list of covariates.

6. Provide plot of PS distributions stratified by treatment group.

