#### **10. Final Power Assessment**

#### Date conducted: 02/09/2022

- 10. Re-calculate power in the appropriate excel table, using the revised number of matched patients from the PS-match in Section 9. All other parameters in the table should be the same as in Section 8.
- 1. Pooled

Superiority Analysis - Pooled					
Number of patients matched	368,214	368,214	368,214	368,214	368,214
Reference	184,107	184,107	184,107	184,107	184,107
Exposure	184,107	184,107	184,107	184,107	184,107
Risk per 1,000 patients	41.4155034	41.4155034	41.4155034	41.4155034	41.4155034
Alpha (2-sided)	0.05	0.05	0.05	0.05	0.05
Desired HR from RCT	0.8	0.7	0.6	0.5	0.4
Number of events expected	15249.7682	15249.7682	15249.7682	15249.7682	15249.7682
Power	1	1	1	1	1

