Heparin Sodium Porcine/Dextrose (5% in water or 5% in water/PF), Heparin Sodium, Program Sodium Porcine, and Warfarin Sodium	
2       Creatine clearance < 15 ml/min calculated with the Cockcroft-Gault formula	
Any contradiction for anticoagulation with apixaban or rivaroxaban as determined by the treating physician such as, but not limited to one of the following:	
Mesaured [-180, 0] in any diagnosis position and in an inpatient setting (transfusion codes required for non-critical sites)	
Maior Bleeding See "Major Bleeding" Sheet	
Active Bleeding     Measured [-180,0] in any diagnosis position in an inpatient setting (transfusion codes not required for non-critical sites)     Clinically Relevant Non-Major Bleeding Events	
See "CRNM Bleeds Sheet"	
Measuered [-180, 0] in any diagnosis position in an inpatient or oupatient setting:           DVT           ICD-9 Diagnosis: 451.1x, 451.2x, 451.81, 451.9x, 453.1x, 453.2x, 453.8x, 453.9x, 453.40, 453.41, 453.42, 453.0           ICD-10 Diagnosis: 180.1x, 180.2, 180.3, 180.9, 182.0, 182.1, 182.2x (except 182.21), 182.4x, 182.6x, 182.80, 182.90, 181.A1x, 182.E1x, 182.C1x	
2) Other Indication for anticoagulation (e.g. mechanical valves, venous thromosis)       PE         ICD-9 Diagnosis:       415.1, 415.10, 415.11, 415.12, 415.13, 415.5, 415.16, 417.17, 415.19, 41	
Prosthetic Heart Valve ICD-9 Diagnosis: V43.3 ICD-10 Diagnosis: Z95.2	

1

	Measured [-180, 0] in prescription claims	
3) Dual Antiplatelet Use	Use of Antiplaelets Any of the following: cilostazol, dipyridamole, ticlopidine HCl, aspirin, clopidogrel bisulfate, prasugrel HCl, ticagerlor, aspirin/dipyridamole, ezetimibe	

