532.6 - CHRONIC OR UNSPECIFIED DUODENAL ULCER WITH HEMORRHAGE AND PERFORATION 532.60 - CHRONIC OR UNSPECIFIED DUODENAL ULCER WITH HEMORRHAGE AND PERFORATION WITHOUT OBSTRUCTION 532.7 - CHRONIC DUODENAL ULCER WITHOUT MENTION OF HEMORRHAGE OR PERFORATION 532.9 - DUODENAL ULCER UNSPECIFIED AS ACUTE OR CHRONIC WITHOUT MENTION OF HEMORRHAGE OR PERFORATION 533.21 - ACUTE PEPTIC ULCER OF UNSPECIFIED SITE WITH HEMORRHAGE AND PERFORATION WITH OBSTRUCTION 533.4 - CHRONIC OR UNSPECIFIED PEPTIC ULCER OF UNSPECIFIED SITE WITH HEMORRHAGE 533.40 - CHRONIC OR UNSPECIFIED PEPTIC ULCER OF UNSPECIFIED SITE WITH HEMORRHAGE WITHOUT OBSTRUCTION 533.41 - CHRONIC OR UNSPECIFIED PEPTIC ULCER OF UNSPECIFIED SITE WITH HEMORRHAGE WITH OBSTRUCTION 533.5 - CHRONIC OR UNSPECIFIED PEPTIC ULCER OF UNSPECIFIED SITE WITH PERFORATION 533.61 - CHRONIC OR UNSPECIFIED PEPTIC ULCER OF UNSPECIFIED SITE WITH HEMORRHAGE AND PERFORATION WITH OBSTRUCTION 533.9 - PEPTIC ULCER OF UNSPECIFIED SITE UNSPECIFIED AS ACUTE OR CHRONIC WITHOUT MENTION OF HEMORRHAGE OR PERFORATION 534.0 - ACUTE GASTROJEJUNAL ULCER WITH HEMORRHAGE 534.1 - ACUTE GASTROJEJUNAL ULCER WITH PERFORATION 534.2 - ACUTE GASTROJEJUNAL ULCER WITH HEMORRHAGE AND PERFORATION 534,21 - ACUTE GASTROJEJUNAL ULCER WITH HEMORRHAGE AND PERFORATION WITH OBSTRUCTION 534.4 - CHRONIC OR UNSPECIFIED GASTROJEJUNAL ULCER WITH HEMORRHAGE 534.5 - CHRONIC OR UNSPECIFIED GASTROJEJUNAL ULCER WITH PERFORATION 534.6 - CHRONIC OR UNSPECIFIED GASTROJEJUNAL ULCER WITH HEMORRHAGE AND PERFORATION 534.60 - CHRONIC OR UNSPECIFIED GASTROJEJUNAL ULCER WITH HEMORRHAGE AND PERFORATION WITHOUT OBSTRUCTION 535.11 - ATROPHIC GASTRITIS WITH HEMORRHAGE 535.30 - ALCOHOLIC GASTRITIS (WITHOUT HEMORRHAGE) 535.50 - UNSPECIFIED GASTRITIS AND GASTRODUODENITIS (WITHOUT HEMORRHAGE) 535.51 - UNSPECIFIED GASTRITIS AND GASTRODUODENITIS WITH HEMORRHAGE 535.60 - DUODENITIS (WITHOUT HEMORRHAGE) 535.61 - DUODENITIS WITH HEMORRHAGE 537.83 - ANGIODYSPLASIA OF STOMACH AND DUODENUM WITH HEMORRHAGE 562.02 - DIVERTICULOSIS OF SMALL INTESTINE WITH HEMORRHAGE 562.10 - DIVERTICULOSIS OF COLON (WITHOUT HEMORRHAGE) 562.12 - DIVERTICULOSIS OF COLON WITH HEMORRHAGE 569.3 - HEMORRHAGE OF RECTUM AND ANUS 623.8 - OTHER SPECIFIED NONINFLAMMATORY DISORDERS OF VAGINA 626.8 - OTHER DISORDERS OF MENSTRUATION AND OTHER ABNORMAL BLEEDING FROM FEMALE GENITAL TRACT 786.3 - HEMOPTYSIS 786.30 - HEMOPTYSIS UNSPECIFIED 786.39 - OTHER HEMOPTYSIS 285.9 - ANEMIA UNSPECIFIED 790.92 - ABNORMAL COAGULATION PROFILE 363.63 - CHOROIDAL RUPTURE 626.2 - EXCESSIVE OR FREQUENT MENSTRUATION 372.72 - CONJUNCTIVAL HEMORRHAGE

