	3,551 (9.0%)	4.451 (6.2%)		863 (2.1%)	2,356 (4.6%) 1.459 (2.9%)		7,918 (5.3%) 5.890 (4.0%)	8.882 (5.0%)		8.577 (3.7%)	24,412 (0.2%)	
Other Comorbidity - Occurrence of chronic renal insufficiency w/o CKD ; n (%)			-0.07 -0.06			-0.05			-0.05 -0.03			-0.06
Other Comorbidity - Occurrence of miscellaneous renal insufficiency; n (%)	2,103 (5.3%) 2,884 (7.3%)	4,886 (6.8%)	-0.06	1,364 (3.3%)	2,249 (4.5%) 2,361 (4.8%)	-0.06	6,344 (4.3%)	8,864 (5.0%)	-0.03	9,811 (4.3%)	15,999 (5.4%)	-0.05
Other Comorbidity - Hypertensive nephropathy; n (%)	=,== (	7,839 (10.8%)		1,129 (2.7%)	=,==: (,)		8,281 (5.6%)	13,721 (7.8%)		12,294 (5.3%)	23,921 (8.0%)	
Other Comorbidity - Obstructive sleep apnea; n (%)	4,313 (10.9%)	7,717 (10.7%)	0.01	5,200 (12.4%)	6,858 (13.9%)	-0.04	9,174 (6.2%)	11,567 (6.6%)	-0.02	18,687 (8.1%)	26,142 (8.8%)	-0.03
Other Comorbidity - Osteoarthritis; n (%)	8,123 (20.5%)	16,520 (22.9%)	-0.06	6,591 (15.7%)	7,983 (16.1%)	-0.01	31,918 (21.4%)	38,031 (21.5%)	0.00	46,632 (20.2%)	62,534 (21.0%)	-0.02
Other Comorbidity - Other arthritis, arthropathies and musculoskeletal pain; n (%)	15,178 (38.4%)	29,550 (40.9%)	-0.05	14,428 (34.4%)	17,421 (35.2%)	-0.02	54,846 (36.8%)	65,149 (36.9%)	0.00	84,452 (36.6%)	112,120 (37.6%)	
Other Comorbidity - Dorsopathies; n (%)	8,826 (22.3%)	17,719 (24.5%)	-0.05	8,294 (19.8%)	10,115 (20.4%)	-0.01	30,828 (20.7%)	38,050 (21.6%)	-0.02	47,948 (20.8%)	65,884 (22.1%)	-0.03
Other Comorbidity - Fractures; n (%)	1,798 (4.5%)	3,589 (5.0%)	-0.02	1,485 (3.5%)	1,806 (3.6%)	-0.01	7,167 (4.8%)	8,538 (4.8%)	0.00	10,450 (4.5%)	13,933 (4.7%)	-0.01
Other Comorbidity - Falls; n (%)	2,265 (5.7%)	5,681 (7.9%)	-0.09	834 (2.0%)	1,462 (3.0%)	-0.06	2,974 (2.0%)	4,471 (2.5%)	-0.03	6,073 (2.6%)	11,614 (3.9%)	-0.07
Other Comorbidity - Sleep Disorder; n (%)	2,301 (5.8%)	2,499 (3.5%)	0.11	3,477 (8.3%)	2,600 (5.3%)	0.12	8,065 (5.4%)	7,074 (4.0%)	0.07	13,843 (6.0%)	12,173 (4.1%)	0.09
Other Comorbidity - Delirium; n (%)	953 (2.4%)	2,815 (3.9%)	-0.09	596 (1.4%)	1,051 (2.1%)	-0.05	3,460 (2.3%)	5,237 (3.0%)	-0.04	5,009 (2.2%)	9,103 (3.1%)	-0.06
Other Comorbidity - Psychosis; n (%)	468 (1.2%)	911 (1.3%)	-0.01	352 (0.8%)	356 (0.7%)	0.01	2,692 (1.8%)	2,582 (1.5%)	0.02	3,512 (1.5%)	3,849 (1.3%)	0.02
Procedures												
Procedure - Hip Surgery; n (%)	258 (0.7%)	327 (0.5%)	0.03	272 (0.6%)	127 (0.3%)	0.04	1,111 (0.7%)	668 (0.4%)	0.04	1,641 (0.7%)	1,122 (0.4%)	0.04
Medications												

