DM Medications - 1st and 2nd Generation SUs ; n (%) DM Medications - DPP-4 Inhibitors; n (%)	2,118 (6.2%) 860 (2.5%)	2,081 (6.1%) 888 (2.6%)	0.004162423 -0.006343679	1,622 (5.2%) 978 (3.2%)	1,634 (5.3%) 979 (3.2%)	-0.004483651	7,542 (6.3%) 3,422 (2.9%)	7,589 (6.4%) 3,455 (2.9%)	-0.00410072	11,282 (6.1%) 5,260 (2.9%)	11,304 (6.1%) 5,322 (2.9%)	0
DM Medications - GLP-1 RA; n (%)	345 (1.0%)	349 (1.0%)	0	452 (1.5%)	454 (1.5%)	0	793 (0.7%)	774 (0.6%)	0.012444223	1,590 (0.9%)	1,577 (0.9%)	0
DM Medications - SGLT-2 Inhibitors ; n (%)	317 (0.9%)	317 (0.9%)	0	387 (1.3%)	384 (1.2%)	0.009000794	524 (0.4%)	519 (0.4%)	0	1,228 (0.7%)	1,220 (0.7%)	0
DM Medications - Metformin; n (%) Other Medications - Use of NSAIDs: n (%)	4,637 (13.6%) 4,170 (12.2%)	4,625 (13.6%) 4,141 (12.2%)	0	3,972 (12.8%) 4 177 (13.5%)	3,996 (12.9%) 4,205 (13.6%)	-0.002988238 -0.002921785	15,017 (12.6%) 15.933 (13.4%)	15,014 (12.6%) 15.888 (13.3%)	0 002940191	23,626 (12.8%) 24,280 (13.2%)	23,635 (12.8%) 24,234 (13.2%)	0
Other Medications - Use of other hypertension drugs; n (%)	2,254 (6.6%)	2,221 (6.5%)	0.004041947	1,668 (5.4%)	1,691 (5.5%)	-0.004405265	8,885 (7.5%)	8,941 (7.5%)	0	12,807 (7.0%)	12,853 (7.0%)	ō
Other Medications - Digoxin; n (%)	2,219 (6.5%)	2,219 (6.5%)	0	2,082 (6.7%)	2,078 (6.7%)	0	10,307 (8.7%)	10,355 (8.7%)	0	14,608 (7.9%)	14,652 (8.0%)	-0.003696624
Other Medications - Use of Anti-arrhythmics; n (%) Other Medications - Use of antipsychotics: n (%)	5,454 (16.0%) 632 (1.9%)	5,437 (16.0%) 603 (1.8%)	0 007421163	6,102 (19.7%) 409 (1.3%)	6,071 (19.6%) 407 (1.3%)	0.002516669	21,156 (17.8%) 3.028 (2.5%)	21,105 (17.7%) 3.074 (2.6%)	0.002617178	32,712 (17.8%) 4.069 (2.2%)	32,613 (17.7%) 4 084 (2.2%)	0.002617178
Other Medications - Use of dementia meds; n (%)	1,093 (3.2%)	1,091 (3.2%)	0	625 (2.0%)	634 (2.1%)	-0.007057056	5,249 (4.4%)	5,267 (4.4%)	0	6,967 (3.8%)	6,992 (3.8%)	0
Other Medications - Use of antiparkinsonian meds; n (%)	857 (2.5%)	861 (2.5%)	0	625 (2.0%)	631 (2.0%)	0	3,737 (3.1%)	3,654 (3.1%)	0	5,219 (2.8%)	5,146 (2.8%)	0
Other Medications - Use of anxiolytics/hypnotics; n (%) Other Medications - Use of anticonvulsants; n (%)	1,623 (4.8%) 3,791 (11.1%)	1,628 (4.8%) 3,820 (11.2%)	0 -0.003177126	1,745 (5.6%) 2,559 (8.3%)	1,763 (5.7%) 2,524 (8.2%)	-0.004331176 0.003634718	7,389 (6.2%) 13,875 (11.6%)	7,356 (6.2%) 13,931 (11.7%)	0 -0.003116982	10,757 (5.8%) 20,225 (11.0%)	10,747 (5.8%) 20,275 (11.0%)	0

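### The Appendix B propensity-score list leaves out several claims-measurable predictors of the bleeding endpoint: outpatient bleeding, anemia, GI disease and acid-suppressant use

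*Combined protocol and SAP*

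**What the plan says.** Section 6.2 uses age, gender and a comorbidity score for feasibility only. It adds that "Remaining covariates are defined only after the study has passed the initial feasibility analysis" and the initial power assessment, and refers to Table 1 in Appendix B for them. Section 9 then tells the analyst to "complete a 1:1 PS-matched analysis" with every listed covariate in the model. Appendix B is therefore the definition of the PS.

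Appendix B contains many bleeding-relevant rows: age, combined comorbidity score, hypertension, ischemic and hemorrhagic stroke, acute renal disease, CKD stages 1 to 3, alcohol, falls, frailty, NSAIDs, oral corticosteroids, antidepressants, and fecal occult blood (FOB) and PT/aPTT testing. The other-medication rows start at "Other Medications - Use of NSAIDs: n" and run to estrogens, progestins and androgens. The comorbidity rows end at "Other Comorbidity - Psychosis; n".

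The bleeding-history exclusion in Appendix A covers major and CRNM bleeding in the prior 180 days. Its CRNM part reads "Measured [-180,0] in any diagnosis position in an inpatient setting (transfusion codes not required for non-critical sites"; the major-bleeding part is also inpatient. The exclusion uses the same code sheets as the outcome. The CRNM sheet is headed as inpatient, any diagnosis, and includes "285.9 - ANEMIA UNSPECIFIED".

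**The concern.** The CRNM sheet counts more than bleeding. It includes unspecified anemia and reflux esophagitis in both coding systems. In ICD-9 it also includes ulcer, gastritis and diverticular codes whose labels say hemorrhage is absent. A patient with known outpatient anemia or reflux esophagitis who is admitted for another reason, with that code in a secondary position, becomes a primary-outcome event. Baseline history of these conditions is therefore a plausible predictor of this endpoint, and the protocol already holds codes for most of it.

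If prescribers take that history into account when choosing a drug, matching on the listed covariates removes the resulting imbalance only as far as the listed rows act as proxies. The pooled interval reflects sampling error alone and is very narrow. Section 13.2, on sensitivity analyses, carries only a heading.

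**Working it through.** **Is the omission real, or lost in the PDF?** Rows are cut at page breaks, so the two Appendix B tables have to be read together. The matched table supplies osteoporosis, dementia and thyroid disease, which are missing from the unmatched one. The unmatched table supplies psychosis, which is missing from the matched one. The medication rows run from meglitinides to estrogens in both. No gap remains where a GI, anemia or acid-suppressant block could sit. Hemorrhagic stroke is the only prior-bleeding row.

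**What does the entry exclusion remove?** Inpatient-coded forms only: 2,721 patients (2%) in Optum, 3,332 (3%) in MarketScan and 23,500 (6%) in CMS (Section 5.3). Outpatient-coded history is neither excluded nor listed as a covariate.

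**The plan's own power.** Section 8 sets power "given the feasibility counts and an alpha of 0.05" and Section 10 keeps those parameters, with "Desired HR from RCT" from 0.8 down to 0.4. For Optum at HR 0.8:
- events = 68,134 × 19.8838767 / 1,000 = 1,354.77
- power = Φ(|ln 0.8| × √(1,354.77 / 4) − 1.96) = Φ(0.2231 × 18.404 − 1.96) = Φ(2.147) = 0.984, matching the printed 0.98409053.

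The same formula gives MarketScan 0.99638561 and 1 for CMS and pooled, as printed.

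**Pooled precision.**
- Events = 368,214 × 41.4155034 / 1,000 = 15,249.77.
- SE(log HR) = 2 / √15,249.77 = 0.0162.
- 95% limits are the HR multiplied or divided by exp(1.96 × 0.0162) = 1.032, or 0.969 to 1.032 at HR 1.
- The database-level expected events in Section 10 sum to 15,613.6, not 15,249.8. The half-width rounds to 3.2% either way.

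**Residual gap needed to move the HR by that half-width.** Bross factor = [1 + p₁(RR − 1)] / [1 + p₀(RR − 1)], where p₀ and p₁ are the post-match prevalences in the two arms. Setting it to 1.0323 gives a gap of 0.0323 × [1 + p₀(RR − 1)] / (RR − 1). Prevalence and RR are assumptions; the documents give neither.

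| Assumed prevalence | RR 1.5 | RR 2 | RR 3 |
|---|---|---|---|
| 5% | 6.6 points | 3.4 | 1.8 |
| 10% | 6.8 | 3.6 | 1.9 |
| 20% | 7.1 | 3.9 | 2.3 |
| 30% | 7.4 | 4.2 | 2.6 |

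**Several small gaps.** Assume four independent factors, each with 10% prevalence, all imbalanced the same way:
- 0.5 points each: (1.105/1.10)⁴ = 1.018 at RR 2; (1.21/1.20)⁴ = 1.034 at RR 3.
- 1 point each: (1.11/1.10)⁴ = 1.037 at RR 2; (1.22/1.20)⁴ = 1.068 at RR 3.

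**Effect on the nominal 95% interval.** Coverage = Φ(1.96 − x) − Φ(−1.96 − x), with x = ln(bias) / 0.0162. It is 0.94 at bias 1.005, 0.91 at 1.01, 0.77 at 1.02 and 0.55 at 1.03.

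**Benchmark from measured covariates.** Before matching, the pooled gaps are 2.2 points for acute renal disease (4.0% rivaroxaban, 6.2% apixaban) and 2.7 for CKD stage 3 (5.5%, 8.2%). An omitted factor that kept such a gap in full would bias the HR by a factor of 1.02 to 1.03 at RR 2 and 1.04 to 1.05 at RR 3. These are upper-type values, because matching on correlated covariates should shrink the gap.

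**The case against.** A reader might infer that the PS misses the main bleeding predictors and that the result will be biased beyond its interval. The documents do not support either.

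- Many strong predictors are in the PS and balance well. After matching, pooled age is 74.07 vs 74.04, comorbidity score 1.91 vs 1.90, and CKD stage 3 6.1% in both arms. Post-match c-statistics are 0.506 to 0.514.
- The entry exclusion uses the outcome's own sheets, so recent inpatient forms of several named conditions are already removed. Liver disease, coagulopathy, cancer and dual antiplatelet use are excluded as well.
- In ICD-10, the CRNM sheet has only bleeding or perforated ulcer codes and only bleeding diverticular codes. The non-bleeding route into the outcome for those two conditions is therefore an ICD-9 matter.
- The nearest listed proxies differ little even before matching (rivaroxaban vs apixaban): FOB test 3.2% vs 3.0%, colonoscopy 4.1% vs 3.8%, NSAIDs 13.4% vs 12.7%, corticosteroids 20.2% vs 21.0%. The directions are mixed. A 0.8-point gap at 20% prevalence gives 1.208/1.20 = 1.007 (RR 2) or 1.416/1.40 = 1.011 (RR 3).
- At 20% prevalence, even a 2-point gap gives 1.017 (RR 2) to 1.029 (RR 3), inside the half-width. A 5-point gap would give up to 1.071, but it exceeds the crude gaps for heart failure (3.6), ischemic stroke (2.7) and CKD stage 3 (2.7).
- At a true HR of 0.8, a 7.1% bias gives 0.857, with an upper limit near 0.857 × 1.032 = 0.885. The conclusion would stand.

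All of this limits the size of the problem. It does not fill the gap: outpatient history of these conditions, and acid-suppressant use, have no listed row. Two doubts remain. The components of the comorbidity score are not given, so it may capture some of this history. The two tables also do not share one row list: the count of distinct diagnoses, a broad morbidity proxy with a pooled standardized difference of −0.31 before matching, has no row in the matched table. Both are reasons to check the source table.

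**Conclusion.** The point holds as a gap in the covariate list. Followed exactly, the plan leaves several claims-measurable predictors of its own endpoint unadjusted: outpatient or ED bleeding, outpatient-coded anemia, ulcer/gastritis/reflux, diverticular disease, and PPI/H2-blocker use. It does not establish that the estimate is biased.

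Whether the interval absorbs the residual imbalance matters mainly when the true HR is near 1. There, one factor needs roughly a 2-point (RR 3) to 4-point (RR 2) post-match gap to match the 3.2% half-width, or several gaps of about half a point to one point in the same direction. Every prevalence, RR and gap here is assumed. The direction is also unknown: most crude differences show sicker apixaban users, which would raise the HR against apixaban, but NSAID use and FOB testing run the other way. The reading of Appendix B rests on text recovered from a PDF and needs the sponsor's confirmation.

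**What to change.** Before any outcome comparison by arm:

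1. Confirm the omission against the source covariate table, and state what the comorbidity score contains.
2. Add to the PS, from the same 180-day claims window: outpatient or ED bleeding codes, outpatient-coded anemia, peptic ulcer/gastritis/reflux, diverticular disease, and PPI and H2-blocker fills.
3. Re-match, and report standardized differences for the new rows before and after matching.
4. Restate matched N and power in Section 10.

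The timing allows this. Section 7 rules out measures of association, Section 10 halts work until balance and power are reviewed, Section 11 invites concerns about residual confounding, and Section 13 carries no analysis date.

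The cost is a few derived covariates, one PS re-run and probably slightly fewer pairs. Every database has power of at least 0.98 at HR 0.8. In Optum, the smallest by expected events, 80% power needs 4 × (1.960 + 0.842)² / (ln 0.8)² ≈ 631 events against 1,354.77 expected, so a modest loss of pairs does no harm.
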